The authors conducted the first systematic, prospective study of resident-to-resident elder mistreatment (R-REM) in nursing homes and have developed novel methodology to identify the phenomenon. Data demonstrated that (1) R-REM is highly prevalent, (2) case finding methodology is greatly enhanced by meaningful participation of front line staff, and (3) paradoxically, higher functioning residents may be at greatest risk for involvement in R-REM (e.g., residents who are ambulatory and capable of wandering as opposed to those who are in the last stages of dementing illness). Additionally, funded by the New York State Department of Health

dementia grants program we developed a three module-program targeting front line staff to implement best practices related to R-REM in long-term services and support (LTSS) settings. Using an experimental design, we tested the intervention in nursing homes. Evaluation of longitudinal outcomes showed significant increases in staff knowledge post training, controlling for pre-training levels for the intervention group and of increased recognition of R-REM, and longitudinal reporting in the intervention as contrasted with the usual care group.¹⁸ Additionally, falls, accidents and injuries were reduced.¹⁹ These findings have important implications for assisted living residences (ALRs) where residents typically have cognitive impairment with better mobility and less staff to intervene in R-REM. The state survey process is also less uniform in ALRs (in comparison to nursing homes) and has not addressed R-REM.

Objectives

The goal of the project is to evaluate a training program for staff that enhances identification and intervention with respect to episodes of resident-to-resident elder mistreatment (R-REM). The hypotheses corresponding to the specific process outcome aims (1 & 2) and primary distal outcome (aim 3) for which the study was powered are:

Aim 1 (A1). Enhance staff knowledge of R-REM

Hypothesis 1: Staff knowledge related to R-REM and R-REM treatment will increase after training.

Aim 2 (A2). Enhance staff recognition, reporting and care planning related to R-REM

Hypothesis 2: Due to the heightened awareness as a result of training, the frequency of reported R-REM in the intervention group will increase, relative to the comparison group after training.

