Aim 3 (A3). Evaluate the impact of the staff intervention on resident falls, accidents and injuries and on quality of life using a prospective experimental design that derives information from five sources: (1) resident interviews (2) staff informants (3) observational data (4) chart and (5) incident/accident report data.

Primary Hypothesis: The frequency of falls, accidents and injuries will decrease in the

intervention group, relative to the comparison group after implementation of the training intervention.

Secondary Hypotheses: 1. Resident quality-of-life as measured by affective state will improve in the intervention group, relative to the comparison group after implementation of the training intervention.

2. Resident behavior problems will decline in the intervention group, relative to the comparison group after implementation of the training intervention. Resident behaviors will mediate the relationship between the intervention and the falls/accidents/injuries outcome.

Trial design

This is a pragmatic, prospective, cluster randomized trial (facility level) design with three waves of data collection (baseline, 6- and 12-months) at 12 assisted living facilities in two New York regions. There will be three levels of clustering: facilities within regions, units within facilities and repeated measures on residents within units, with the regions fixed. On a rolling basis, six facilities will be selected at random and recruited in New York City and the nearby suburban counties (downstate region). Six facilities in the upstate New York region of Rochester will also be randomly selected. Three facilities in each region will be randomized to usual care or to the intervention on a 1:1 ratio. Facilities allocated to the usual care group will receive the intervention after completion of their 12 month data collection.

Methods: Participants, interventions and outcomes

Study setting

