There are no predetermined criteria for discontinuing or modifying the intervention.

Strategies to improve adherence to interventions

Each session is scheduled twice for all shifts, including the night staff. Additional makeup sessions are available for those staff unable to attend the original training sessions. Facility administrators alert the staff of the mandatory training sessions using several methods including flyers posted in the staff room and notices in pay stubs.

Relevant concomitant care permitted or prohibited during the trial

None

Provisions for post-trial care

There are no such provisions for this non-invasive minimal risk intervention for ALR staff.

Outcomes

Aim 1: Process level 2 evaluation of staff knowledge outcomes: Knowledge tests: Ten question pre-post knowledge tests were developed for each of the first two R-REM training modules, i.e., Recognition and Risk Factors, and Management (the SEARCH approach) based on its respective content. An additional knowledge test was developed for the third module: Implementation Guidelines, in order to assess use of the BRDS to document R-REM events. The latter test compares staff answers to the gold standard ratings. Hypothesis 1, regarding enhanced staff knowledge will be examined for individual knowledge items using paired t-tests, comparing pre-post knowledge scores between groups, adjusting standard errors for clustered data within

facilities. Group differences in total scores will be examined using a linear mixed (fixed and random effects) model for effect estimation.

Aim 2: Process level 3 evaluation of implementation outcomes: Recognition and reporting using the R-REM Measures: R-REM behavior recognition and documentation sheet (BRDS):

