This measure was based on the Shift Coupon, a form originally designed by nursing staff to provide a “quick, easy, anonymous, and non-threatening method to report adverse events,”²¹ and is in the form of a small note pad. BRDSs are intended to measure recognition and capture real time R-REM events. Hypothesis 2, regarding enhanced R-REM recognition will be examined with a Chi-square analysis comparing counts of BRDS reports from experimental and comparison facilities captured over time, and treated as binary incidents. Reporting implementation will be examined by evaluating the differences between experimental and comparison group staff reports of R-REM, collected over three waves. Individual R-REM reporting will be determined by counting whether any of the staff-reported R-REM indicators are positive. The object of this analysis is not to identify individuals and perpetrators, but to examine the reported events. In modeling R-REM events, a Poisson regression of count data will be performed.

Aim 3: Primary level-4 evaluation of distal outcomes: Summary of the sources of data for determining falls/accidents/injuries and incidents of R-REM: The data used for evaluation of the primary distal outcome and for R-REM reports include (a) self-report among those residents who are capable, (b) Accident and Incident Reports, (c) resident record review, (d) observational data, including the BRDS, and (e) reports from staff. In addition, an environmental evaluation will occur. Data for falls and injuries will be collected via chart review, staff report and residents who can self-report, and from Incident/Accident Reports on an ongoing basis. Resident and staff informant information will be collected at baseline, 6- and 12-month follow-up. Falls will be considered as binomial (any fall) and Poisson distributed (fall counts).

Sample size {14}

Power calculations are provided for the primary distal outcome: falls, including accidents and injuries, also the outcome requiring the largest sample size. Upstate it is expected that an average

of 50 residents per site will be selected for a total of 300. Downstate, the facilities are larger, and it is expected that the average size will be 125 residents or 750 total. The proposed sample size is 6 facilities and 525 residents per arm.

Using the canonical link (Logit), the generalized linear model (GLIMMIX):

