Algorithms for conducting randomization that take into account clustering such as exists with geographical regions and rolling enrollment have been developed by the author. This method has yielded balanced groups for many studies. This randomization procedure will be carried out using a SAS macro after a facility completes the baseline interview. A random number from 0 to 1 will be used to determine the assignment group. The standard cut score will be set at 0.5 for the first n facilities from the same region. Facilities which receive a random number between 0 and 0.5 will be assigned to the usual care group and those with a random number greater than 0.5 will be assigned to the intervention group. The balance between the groups within each group will be carefully weighted after the total number of facilities from a group reaches a number greater than n. Before the randomization procedure, the number of facilities randomized to each arm for each region will be estimated using SAS macro programs. If more than the n facilities are randomized initially, the cut score for the next facility is equal to the ratio of the intervention group (n1) to the facilities already randomized (m) for that group (n1/m). For example, group A region provides eight facilities for randomization and the n is set to 5, the first five facilities (n) will be randomized to the standard cut score 0.5 (about half will go to the intervention and half to the usual care group). The sixth facility's randomization cut score is equal to the number of facilities in the intervention

group (n_1) divided by the total number of facilities randomized within that group (in this case, the denominator m is 5.) The seventh facility's cut score will be adjusted according to the previous six facilities, and so forth.

Concealment mechanism

The biostatistician who runs the randomization procedure passes the information directly to the intervention trainer who alerts the ALRs of their assignment. The principal investigator who oversees the data coordinating centre (DCC) at the Research Division, Hebrew Home at Riverdale (RD-HHAR) is the only other person made aware of the assignment.

Implementation

A biostatistician at the coordinating centre developed and runs the randomization procedure. Randomization occurs at the facility level. Research interviewers who enrol participants are blinded to randomization group.

Assignment of interventions: Blinding

Who will be blinded

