A. For each participant, ten five-minute observations are performed by trained interviewers at different times of the day and in different locations in order to obtain additional information about incidents of R-REM and other disturbed behaviours. While episodes of R-REM are likely to be brief and intermittent, based on our experience in the nursing home study, interviewers did observe many incidents of R-REM. The Total Observation Checklist includes 14 affect and 37 behaviour items (Observed Behavior Checklist).⁵³ Frequencies of affective and behavioural states are coded as: “Not at all”, “Very little (1 or 2xs during observation period)”, “With some frequency (several times)”, “With moderate frequency (many times but not continuous)”, or “With great frequency (continuous)”. Typical affect items include: “Crying”; “Agitated”; “Emotionally labile”. Typical behavioural items include: “Disruptive of others”; “Wandering”; and “Argumentative”. In an urban LTSS sample, the Cronbach’s alphas ranged from .74 to 0.85 and from 0.85 to 0.87 in a rural LTSS sample.⁵⁴

B. R-REM behavior recognition and documentation sheet (BRDS): This measure was based on the Shift Coupon, a form originally designed by nursing staff to provide a “quick, easy, anonymous, and non-threatening method to report adverse events,”⁵⁵ and was in the form of a small note pad. BRDSs are intended to measure recognition and capture real time R-REM events. These forms are designed as prescription pads to be carried in the pockets of staff. They are distributed at the training sessions (module 3 for intervention facilities and during the opening of the unit for usual care staff); additional pads are available at a central location. Sheets are torn off after documenting R-REM. Items include: residents involved, identity of the perpetrator, actions involved, location, potential cause, and what did you (staff) do about it. Boxes for completed forms are placed in a designated location on each unit.

C. Event logs: When an event is reported from a) resident interview b) staff interview c) interviewer observation, or d) BRDS, the research interviewer will complete an Event Log worksheet in order to better understand the circumstances of the R-REM event. This form contains descriptive

information about the event, its time and place, the reporting source, the participants, and environmental factors at the time of the event.

4. Chart data

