Demographic variables of interest include age, race, educational attainment, and length of stay in the facility. Medical diagnoses, medications, activities of daily living, cognitive impairment and mental health data will be extracted from the Assisted Living Residence Medical Evaluation form. Diagnosis information will be integrated into a comorbidity index, in order to adjust for burden of chronic illnesses. Interrater reliability will be examined on a random subset of charts. In addition, physical function, including history of falls in the past 3 months, frequency of falls, resulting injuries and open-ended comments and behavioral issues data will be extracted from the Assisted Living Resident Evaluation Form that is completed at admission. The resident Individual Service Plan will be reviewed for reports of occurrences of R-REM, falls, incidents and injuries and other covariate information that develop from three months prior to baseline through the study end.

5. Accident/ Incident Reports

The New York State Department of Health mandates electronic transfer of accident and incident reports to regional offices as part of licensing standards for ALRs statewide. Federal regulations require the reporting of alleged violations of abuse, mistreatment and neglect, including injuries of unknown origin to the facility administrator and in accordance with state law. The reports will be reviewed for potential incidents of R-REM and falls. Data will be collected from three months prior to the study through the end of data collection. Each incident report reviewed for resident falls/ accidents/ injuries may also contain evidence of R-REM.

6. Environmental Assessment

In addition, physical environment is assessed (direct assessment at local site): The modified Therapeutic Environment Screening Scale (TESS)⁵⁶ will be used by research staff to measure the physical environment. The TESS includes 12 domains: unit autonomy, exit control, maintenance, cleanliness, safety, lighting, space/seating, physical appearance/homeliness, access to outdoors, orientation and cuing, privacy, and noise, and a scale measuring quality. These data will

be collected for descriptive purposes, and for possible inclusion in hierarchical linear models.

Facility and unit characteristics will also be collected.

Plans to promote participant retention and complete follow-up

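### Aim 2: the chi-square on BRDS report counts and the Poisson regression of R-REM events state no adjustment for facility clustering

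*Combined protocol and SAP*

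**What the plan says.** Under Outcomes, Aim 2, Hypothesis 2 (more reported R-REM in the intervention group after training) is to be examined by a "Chi-square analysis comparing counts of BRDS reports from experimental and comparison facilities captured over time, and treated as binary incidents". The same paragraph adds: "In modeling R-REM events, a Poisson regression of count data will be performed". It mentions no random effect, robust standard error, overdispersion term or exposure offset for either analysis, and it does not define the unit or denominator of the chi-square.

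The design is clustered. Under Implementation of the allocation: "Randomization occurs at the facility level". Under Trial design: "Three facilities in each region will be randomized to usual care or to the intervention on a 1:1 ratio". The Trial design section also lists facilities and units as levels of clustering.

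The neighbouring analyses allow for this:

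- Aim 1 is tested by "comparing pre-post knowledge scores between groups, adjusting standard errors for clustered data within" facilities.
- The falls model has random effects for facilities, units and subjects.
- The mixed models for secondary outcomes allow for correlation within units and facilities.

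The Objectives section separates the "specific process outcome aims (1 & 2) and primary distal outcome (aim 3"), so Aim 2 is a stated hypothesis but not the primary one.

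**The concern.** An ordinary chi-square or Poisson regression treats each report, or each resident, as independent. Staff in one facility share management, routines and reporting habits, so reports from the same facility are likely to be correlated. Allocation is by facility, so that correlation goes straight into the variance of the difference between arms, and an unadjusted test leaves it out. A significant result could then reflect which facilities happened to fall in which arm rather than the training. Variation purely between regions cancels if each region is split 3:3; variation between facilities within a region does not.

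**Working it through.** **The plan's own design effect.** The Sample size section gives, for falls, 17 residents per unit, unit ICC 0.03, 5 units per facility and facility ICC 0.015. Then 1 + 16 × 0.03 + 4 × 17 × 0.015 = 1 + 0.48 + 1.02 = 2.50, the stated value. (The printed formula carries a further factor p_e; 2.5 follows without it.) With falls rates of 33% and 20.75%, two follow-up waves, two-sided 5%, 80% power and reliability 0.95, the plan's formulas give 403.4 and 430.3 (Diggle; stated 404 and 431) and 398.0 and 424.5 (GEE; stated 399 and 425). The falls figures therefore reproduce. No corresponding calculation is given for Aim 2.

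**Error of an unadjusted test.** For a nominal two-sided 5% test and design effect DE, true error = 2 × [1 − Φ(1.96/√DE)]. Let w be the share of between-facility variance that lies within region, with 3:3 allocation in each region. ICCs and CVs for BRDS reports are assumptions throughout.

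*Resident as unit.* 525/6 = 87.5 residents per facility, so DE = 1 + 86.5 × ICC × w.

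| Assumed ICC | DE, w = 1 | Error | DE, w = 0.5 | Error |
|---|---|---|---|---|
| 0.005 | 1.43 | 10% | 1.22 | 7.6% |
| 0.015 | 2.30 | 20% | 1.65 | 12.7% |
| 0.03 | 3.60 | 30% | 2.30 | 19.6% |
| 0.05 | 5.33 | 40% | 3.16 | 27.0% |

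*Falls ICCs carried over.* DE = 1 + 16 × [0.03 − 0.015 × (1 − w)] + 68 × 0.015 × w. At w = 1, DE = 2.50 and 1.96/√2.50 = 1.24, so error is 21.5%. At w = 0.5, DE = 1.87 and error is 15.2%.

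*Report sheet as unit.* With an assumed 20 sheets per facility and between-facility coefficient of variation CV, DE = 1 + 20 × CV² × w.

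| Assumed CV | DE, w = 1 | Error | DE, w = 0.5 | Error |
|---|---|---|---|---|
| 0.10 | 1.20 | 7.4% | 1.10 | 6.2% |
| 0.25 | 2.25 | 19.1% | 1.625 | 12.4% |
| 0.50 | 6.00 | 42.4% | 3.50 | 29.5% |

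In the resident and sheet cases, w = 0 gives DE = 1 and error 5%. More sheets make it worse: with 50 per facility and w = 1, the three CVs give 11%, 33% and 59%.

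**Simulation check** (null trials, 12 facilities, 3:3 per region).

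- Sheets, 100,000 trials: the pooled chi-square rejected in 7.4%, 19.1% and 42.1% at w = 1; 6.1%, 12.5% and 31.6% at w = 0.5; and 4.9–5.0% at w = 0.
- Residents, 40,000 trials, assumed 20% event rate, 88 per facility: 10.1%, 19.5%, 30.2% and 39.9% at w = 1.
- Residents with the plan's facility sizes of 50 and 125: 11.1%, 22.1%, 33.6% and 43.2% at w = 1, so the equal-size table is slightly favourable to the plan.
- A region-stratified facility-level t-test (12 − 4 = 8 df) stayed at 4.8–5.9% in every setting.
- An uncorrected sandwich z-test with no region term gave 10.4–11.0% on sheets at w = 1. With 12 facilities, clustered standard errors alone are not enough.

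**The case against.** The strongest reply is that the plan already has a general rule. Under Statistical methods for primary and secondary outcomes, one sentence says that binomial tests for dichotomous data and Poisson tests for counts adjust standard errors for clustering within facilities. Those are the two data types used in Aim 2. Reading it as a rule for baseline comparisons only is awkward: it says p values are reported, whereas later in the same section baseline variables are to be shown by arm without p values.

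That makes the scope of the sentence uncertain; it does not settle it. The sentence stands under the lead-in for the primary falls hypothesis and follows the text on checking baseline balance. It names neither the chi-square, the BRDS nor Aim 2, and gives no small-sample correction. The baseline-adjusted mixed models do not fill the gap either. The listed secondary outcomes are affect, depression and behavior. Intervention facilities receive BRDS pads only at module 3, after baseline data collection, so they have no baseline BRDS value to adjust for.

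Two other points stand. No particular error rate can be claimed, because the ICCs, CVs and sheet counts are assumed and the range is wide. And the different start of BRDS collection in the two arms is a separate measurement matter that cluster adjustment would not cure. It is included below because any facility rate needs a defined exposure.

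**Conclusion.** The concern holds. As written, the Aim 2 chi-square and Poisson regression do not account for the unit of randomisation, and their type I error exceeds 5% whenever reports are positively correlated within facilities beyond what region explains. Over the assumed values for residents or 20 sheets per facility, error runs from 5% (all variation regional) to about 42% (CV 0.50, all within region). Borrowing the plan's falls design effect gives 21.5%. The direction is secure; the size depends on variation that the documents do not quantify. It should be fixed before analysis, but it bears on a process hypothesis and leaves the primary falls inference untouched.

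**What to change.** - Replace the chi-square with a comparison of the 12 facility BRDS rates, stratified by region, using a t or permutation test. Alternatively, fit an overdispersed count model with a facility effect, a region term, an exposure offset and facility-level degrees of freedom.
- Apply the same facility clustering to the Poisson regression of R-REM events.
- State the BRDS unit and denominator, and count sheets over the same post-randomisation window in both arms. Under Observational Data, item B, the pads start at different points: "They are distributed at the training sessions (module 3 for intervention facilities and during the opening of the unit for usual care staff").
- If the sentence on clustered standard errors was meant to cover Aim 2, say so and name a small-sample correction for 12 facilities.

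The change is to the analysis plan, plus two data items: pad start dates and a facility census for the offset. The Environmental Assessment section says "Facility and unit characteristics will also be collected" but does not name these two.

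The statistical price is wider Aim 2 intervals, with about 8 to 10 degrees of freedom. At 8 df and 20 sheets per facility, the width relative to the unadjusted interval is (2.306/1.96) × √(1 + 20 × CV² × w). For CV 0.10, 0.25 and 0.50 this is 1.3, 1.8 and 2.9 times if all variation is within region, and 1.2, 1.5 and 2.2 times if half is.

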- 1) If the resident has a perceptual impairment that makes it difficult for her/him to read/sign the Informed Consent Form (e.g., visual impairment)
- 2) If the resident is illiterate, the interviewer reads the Informed Consent Form to the resident

3) If the resident has a physical impairment that prevents her/him from writing (e.g., contractures in both arms, paralysis, etc.)

4) If the resident does not wish to sign the Informed Consent Form, but verbally indicates that s/he is willing to participate in the interview

Per the IRB, in these cases, an observer not associated with the research (e.g., facility staff) must witness the verbal consent process.

Interventions

Explanation for the choice of comparators

After successful implementation of the R-REM research protocol in nursing homes, the authors wanted to further test the intervention in another LTSS setting with a similar population but with less staffing and state oversight. Assisted living was selected because it is an area of LTSS that is growing rapidly both in numbers of facilities and in terms of the populations served.

Intervention description

The intervention, i.e., the training of nursing, social work, administrative and other staff on R-REM is conducted in three separate sessions: 1) Recognition and Risk Factors, 2) Management, and 3) Implementation of Guidelines. The trainer who administers the three modules is an experienced doctoral level, adult education professional who participated in the development and modification of the modules; she has extensive experience in staff training. Modules are provided to facilities randomized to the intervention after the completion of baseline data collection, and to those randomized to usual care after completion of 12-month follow up data collection.

Description of Module 1: Recognizing R-REM: Module 1 covers the extent of R-REM which includes: evidence; risk factors associated with the victims, perpetrators, and environment; and the role of cognitive impairment. Different forms of mistreatment are covered, including physical, psychological, sexual, and theft. This module is delivered in the form of an experiential half-hour in-service training, plus pre- and post-tests designed to be conducted at the ALRs.

Description of Module 2: Management of R-REM

- A. Introduction and review of previous session and pretest
- B. Film on management of elder mistreatment

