Statistical models: The primary endpoint analysis for comparison between the two groups with respect to various outcomes will be based on models for the outcome at 6 and 12 months as a function of the intervention condition, adjusting for the baseline value of the outcome, i.e. an ANCOVA-type MEM analysis with intervention as a factor with two levels and baseline value as a covariate. For multiple outcomes (e.g. NIH PROMIS and FTQ) MANCOVA-type MEMs will be used to simultaneously model the multiple outcome variables. An additional factor (domain) denoting the individual outcome variables will be included in the model together with interactions between domain (depression/affect measures) and intervention. A significant interaction term would indicate that the effect of the treatment is different for affect and depression; in that case two treatment effects will be estimated for each outcome. If the interaction is not significant a model with only main effects for depression/affect and treatment will be fit and the (common) treatment effect will be estimated from this model. In addition to significance testing, we will estimate the treatment effects with 95% CI. The MEMs allow modeling the correlation between the variables assessed on the same subject and that between subjects from the same units and facilities. Group differences in total scores will be examined using a linear mixed (fixed and random effects) model for effect estimation.

The use of SAS Proc MIXED will allow for the possible group heterogeneity in residual variances that may require modeling to satisfy model assumptions and improve model fit, and the modeling of the covariance structure. In secondary analyses, we will examine within subjects change over time. We did not perform power calculations for the secondary outcomes because the most

stringent power requirements are for the primary outcome. However, we will be able to detect relatively small effect sizes, given the sample size.

Examination of the exploratory potential mediating effects of behavior on the relationship between the R-REM intervention and the falls/injuries/accident outcome will be examined using mediation analyses. Although recent evidence from Monte Carlo studies support simple joint significance tests of the mediating path coefficients,^{70,71,72} also examined will be other formal tests of mediation effects.^{73,74}

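### The Aim 2 staff-report analysis spans a pre-training wave and names no baseline covariate, arm-by-time contrast or facility effect, so its wording permits a diluted and poorly calibrated test

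*Combined protocol and SAP*

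**What the plan says.** - **Hypothesis (Objectives, Aim 2).** Hypothesis 2 is that "the frequency of reported R-REM in the intervention group will increase, relative to the comparison group after training".
- **Waves (Trial design; Outcomes, Aim 3).** The design has "three waves of data collection (baseline, 6- and 12-months) at 12 assisted living facilities". On the staff interview: "Resident and staff informant information will be collected at baseline, 6- and 12-month follow-up".
- **Timing (Intervention description; Sequence generation).** "Modules are provided to facilities randomized to the intervention after the completion of baseline data collection". The randomization itself is run "after a facility completes the baseline interview". The staff version of the R-REM interview asks about the preceding two weeks, so the baseline staff report covers only time before training.
- **Aim 2 analysis (Outcomes, Aim 2).** Hypothesis 2 is assigned by name to a chi-square test on the documentation sheets (BRDS). Reporting is then examined by "evaluating the differences between experimental and comparison group staff reports of R-REM, collected over three waves". The text adds: "In modeling R-REM events, a Poisson regression of count data will be performed". It mentions no baseline value, time term, arm-by-time contrast, restriction to follow-up waves, or facility or unit effect.
- **Other analyses (Statistical methods for primary and secondary outcomes).** The falls model has arm, time, their interaction, baseline falls, and random effects for facility, unit and subject. The paragraph headed Statistical models bases the endpoint comparison on "models for the outcome at 6 and 12 months as a function of the intervention condition, adjusting for the baseline value of the outcome". It follows the list of secondary outcomes (affect, depression, behavior) and uses affect and depression as its examples.

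**The concern.** The hypothesis is about what happens after training, yet one of the three waves compared cannot contain a training effect. The terms that would deal with this are written out for falls and for the secondary outcomes but not for Aim 2, which has its own analysis text and its own model.

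Two things are at stake. If the three waves are summarised by one arm effect, the post-training effect is averaged with a wave where it is zero, and a useful programme can look weaker than it is. And with only 12 facilities, chance differences in how readily facilities report are likely. If these are neither adjusted for at baseline nor carried as a random effect, they shift the arm estimate in either direction while the standard error ignores them.

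The staff interview matters here because it gives a baseline in both arms. The BRDS pads reach intervention staff only at the third training module, so they give no pre-training level there.

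**Working it through.** **Inputs**
- Retention: 15% attrition at 6 months and up to 40% at 12 months (Plans to promote participant retention), so relative record counts are 1, 0.85 and 0.60.
- Two-sided alpha of 0.05. The 80% power used below is a reference point only.
- Correlation *r* of reporting levels between waves: not given for staff reports. Assumed 0.3 to 0.8. The falls calculation uses 0.5 and 0.6.

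**The plan's own figures.** No sample size or power is given for Aim 2. The falls table does reproduce, with two follow-up waves, inflation 2.5 and reliability 0.95. The Diggle formula gives 403.4 and 430.3 (stated 404 and 431), and the GEE formula 398.0 and 424.5 (stated 399 and 425). These figures say nothing about staff reports.

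**Step 1: dilution if the waves are pooled.** Pooling Poisson counts averages rates arithmetically:

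pooled ratio = (1 + RR × (0.85 + 0.60)) / (1 + 0.85 + 0.60)

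- RR 1.5: (1 + 1.5 × 1.45) / 2.45 = 1.30
- RR 2.0: (1 + 2.0 × 1.45) / 2.45 = 1.59

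With no attrition the results would be (1 + 2 × 1.5)/3 = 1.33 and (1 + 2 × 2.0)/3 = 1.67.

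**Step 2: power against a test on the two follow-up waves.** On the log scale the retained share of the effect is k = ln 1.296 / ln 1.5 = 0.639, or ln 1.592 / ln 2 = 0.671. With equal wave variances, a weighted mean over waves has variance proportional to Σw² + r(1 − Σw²). Σw² is 0.347 for three waves (weights 0.408, 0.347, 0.245) and 0.515 for two (0.586, 0.414).

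| r | variance, three waves | variance, two waves | SE ratio s |
|---|---|---|---|
| 0.3 | 0.543 | 0.660 | 0.907 |
| 0.8 | 0.869 | 0.903 | 0.981 |

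Power = Φ(2.802 × k / s − 1.96):
- RR 1.5: 51% (r = 0.3) to 45% (r = 0.8)
- RR 2.0: 54% (r = 0.3) to 48% (r = 0.8)

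**Step 3: what baseline adjustment adds.** Take equal waves and a post-training effect d. The pooled contrast has effect 2d/3 and variance (1 + 2r)/3. Follow-up only has effect d and variance (1 + r)/2. Follow-up adjusted for baseline has effect d and variance (1 + r)/2 − r². Where the adjusted analysis has 80% power, follow-up only has 63% (r = 0.5) or 55% (r = 0.6), and the pooled contrast 37% or 30%. The comparator differs from step 2, so the two sets of figures should not be mixed.

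**Step 4: no facility term.** If the true variance is 2.5 times the one the model uses (the inflation stated for falls, borrowed here), a nominal 5% test rejects a true null with probability 2 × (1 − Φ(1.96/√2.5)) = 2 × (1 − Φ(1.24)) = 21.5%.

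**Step 5: simulation.** Twelve facilities of 50 or 125 residents, the attrition above, and 4,000 runs. Assumed: 0.3 reports per resident-wave, and log-normal facility variation with stable SD 0.2 / 0.4 / 0.6 and facility-by-wave SD 0.1 / 0.2 / 0.2.

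| Analysis | Rejection, RR = 1 | Rejection, RR = 1.5 |
|---|---|---|
| Ordinary Poisson, three waves pooled | 35 / 63 / 75% | not interpretable |
| Facility level, three waves pooled | about 5% | 36 / 15 / 10% |
| Facility level, follow-up only | 5 to 6% | 63 / 28 / 17% |
| Facility level, follow-up adjusted for baseline | about 5% | 68 / 44 / 38% |

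The pooled ratio averaged about 1.29 and the adjusted one about 1.50.

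**The case against.** The strongest reply is that the Aim 2 text describes when data are collected and does not fix a contrast. Evaluating arm differences over three waves also fits an arm-by-time analysis, which would not dilute anything. Hypothesis 2 itself points to the post-training contrast. The Statistical models paragraph speaks of various outcomes, and later text rules out covariates other than baseline values in the main analyses, which presupposes baseline adjustment. The primary-outcome section also mentions Poisson tests for counts with standard errors corrected for facility clustering.

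Much of this stands. A reader might infer that the plan commits to a pooled, unadjusted test; it does not, and pooling is only one reading that the wording allows. But none of the other text closes the gap. The baseline-adjusted model is tied to the secondary outcomes, and the clustering remark sits in a paragraph on baseline balance under the primary hypothesis. The Aim 1 text states its own clustering correction, and Aim 2 has no counterpart.

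Three further readings also go too far:
- That this is the main process outcome. No document ranks it so, and Hypothesis 2 is assigned to the BRDS test.
- That power would fall to about 38%. This multiplies the effect by 1.45/2.45 = 0.59 and holds the standard error fixed, but an added wave lowers the variance, and pooled rates average arithmetically.
- That the only harm is a missed effect. With no facility term, false positives are just as much in prospect.

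**Conclusion.** The point holds as an under-specified analysis whose wording permits a poor test, where a better one is available from data already planned. If the waves were pooled, rate ratios of 1.5 and 2.0 would read about 1.30 and 1.59, and a follow-up-only test with 80% power would drop to roughly 45% to 54%. The first pair rests on the plan's attrition figures. The second also assumes equal wave variances and a between-wave correlation of 0.3 to 0.8. Neither applies if an arm-by-time contrast is what the sponsor intends.

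The false-positive risk depends on the missing facility term and not on pooling alone. Its size (21.5% with the borrowed inflation factor, 35% to 75% in simulation) depends on assumed facility variation and shows the direction, not a forecast.

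**What to change.** In the Aim 2 analysis text, state that the arm effect is estimated on staff-reported R-REM at 6 and 12 months, with baseline staff-reported R-REM as covariate, in a Poisson mixed model with random effects for facility and unit and a resident effect for repeated waves. If all three waves are kept as outcomes, make the test the arm-by-post-training contrast, not the arm main effect. Both forms are consistent with the models the plan already sets out for falls and the secondary outcomes.

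The cost is analysis wording only, since the baseline staff interview is already collected. If a facility baseline rate is added as a further covariate, it uses one facility-level degree of freedom out of the few that 12 facilities provide. The BRDS chi-square test is a separate analysis and is not changed by this.
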